#### 4. Study Population

The eligibility criteria for the MyNewOptions Study aim to identify women who are not currently pregnant and not intending pregnancy for at least the next 12 months. All participants will be privately insured through Highmark Health and range in age from 18 to 40.

##### 4.1. Eligibility Criteria

Eligibility is established via an online screening tool. Eligibility criteria are as follows:

- **Highmark Health Member:** Only members of Highmark Health will receive an invitation and are eligible to participate.
- **Age:** Individuals 18-40 years old are eligible.
- **Gender:** Only women are eligible.
- **Sexually Active:** Women must have been sexually active with a male partner in the past 6 months or anticipate being sexually active in the next 6 months.
- **Residence:** Participants must live in the state of Pennsylvania at the time of the eligibility screening and baseline survey completion.
- **Race and Ethnicity:** All racial and ethnic groups are eligible for the study.
- **Pregnancy Status:** Participants may not be pregnant or planning to become pregnant at the time of enrollment until at least 12 months after joining the study.
- **Willingness to participate:** Participants must be willing to give informed consent, be willing to be randomized to the RLP, the RLP+ or the control intervention, and to follow the protocol for the group to which they have been assigned.

##### 4.2. Exclusion Criteria

Women will not be eligible to join the study if they have had a tubal ligation, a hysterectomy, their partner has had a vasectomy, or if they are unable to read and write English.

## **5. Recruitment and Retention**

### **5.1. Recruitment**

The recruitment goal of the MyNewOptions study is to enroll 972 participants over a six-month period. Highmark Health will identify members with prescription medication coverage who meet the following criteria: 18-40 years of age, women, reside in Pennsylvania, are not covered by an employer group with a religious exception, and have not had a previous Highmark claim for a tubal ligation, hysterectomy, or infertility-related service. Highmark will identify a random sample of 15,000 members who meet these criteria and invite them to participate in the MyNewOptions study by mailing the following recruitment material: 1) a pre-invitation postcard, 2) a study invitation (one week following the postcard), and 3) a reminder (two weeks following the study invitation). The study invitation and reminder will be mailed in sealed envelopes with Highmark's return address visible on the outside. Both the invitation and reminder will include a unique invitation code that links to the list of eligible women, maintained by Highmark Health. Mailings will invite women to visit the MyNewOptions website to learn more about the study, or to call study staff at the Penn State College of Medicine if they have questions. Trained research staff will monitor phone, email and website generated questions and respond to each inquiry within one business day. Study enrollment must be completed online.

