### 3. Overview of Trial Design

#### 3.1 Design

MyNewOptions is a two-year, three-arm parallel group design randomized controlled trial testing a Reproductive Life Planning web-based intervention (RLP) vs. a Reproductive Life Planning plus action planning intervention (RLP+) vs. an information only control group.

The inclusion criteria are (1) women; (2) privately insured through Highmark Health; (3) age 18 – 40; (4) Pennsylvania residents; (5) not covered by an employer group with a religious exemption; (6) Internet access; (7) sexually active (within the past 6 months or expected in the next 6 months); and (8) wish to avoid pregnancy for at least the next 12 months. Women were excluded if they had a tubal ligation, hysterectomy, a partner with a vasectomy or if they are unable to read and write English.

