#### **5.1.1. Screening Process**

The homepage of the My New Options study website will include a written and video description of the study. Women will be prompted to enter their unique invitation code at a designated spot on the study homepage if they are interested in proceeding. The code will be required to gain entry past the homepage of the study website. This authentication process is designed to ensure that only women invited to be in the study are able to enroll and participate. Potential participants will then view the study details, eligibility criteria, and the consent documents. Women who indicate interest in proceeding will be directed to REDCap (Research Electronic Data Capture), a secure, web-based application designed exclusively to support data capture for research studies (Harris et al., 2009), where eligibility will be assessed (criteria listed above).

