### 11.2.3.2. Contraceptive adherence

Contraceptive adherence will be classified as high, medium, and low using self-report and pharmacy claims data, depending on the type of contraception being used. For women who have had a sterilization procedure (male or female) or LARC initiation since study enrollment, adherence will be categorized as high. For coital-dependent methods, standard self-reported adherence measures will be used to define adherence categories as shown in Table 3.

Table 3. Definition of Contraceptive Adherence

Methods	Measurement	Definitions	Adherence Category
Sterilization or LARCs (i.e., IUD, contraceptive implant)	Self-report	Adherence assumed	High
Coital dependent methods (i.e., spermicides, withdrawal, sponge, condoms, diaphragm, fertility awareness methods)	Self-report: What percent of time did you use your birth control method during sex in the past 6 months?	Always (100%)	High
		Most of the time (71-99%)	Medium
		Often (51-70%)	
		Sometimes (31-50%)	Low
		Occasionally (1-30%)	
Never (0%)			
Oral contraceptives, contraceptive patch, contraceptive ring, DMPA	Pharmacy claims data: Medication Possession Ratio	MPR >90%	High
		MPR 80-90%	Medium
		MPR <80%	Low

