While self-report measures of oral contraceptive adherence have been the standard in research of this type, self-report has been poorly validated against electronic medication monitors and biochemical assays of medication metabolites. In light of this, we will measure adherence to prescribed contraceptives (i.e., oral contraceptives, patch, shot (DMPA), or ring) using *pharmacy claims data* through Highmark to determine medication possession ratios (MPR). The MPR is the sum of days supply for all prescription fills in the study period, divided by the number of days in the study period. Using pharmacy claims data in this manner can help characterize poor adherence to prescribed medications, including hormonal contraceptives. Since direct observation of medication use is not possible in this study, acquisition of timely refills serves as an appropriate surrogate. Medication adherence has generally been accepted to be an MPR>80%, however this is likely too low when studying contraception. Thus, we will define high (MPR>90%), medium (80-90%), and low adherence (<80%) categories. Highmark preliminary data shows that 6% of members disenroll annually. For participants who are no longer enrolled in Highmark, we will be unable to obtain MPR data for prescription contraceptives. In those cases we will use retrospective self-report measures on contraceptive compliance over the past 6 months. A recent study shows that retrospective report of oral contraceptive use in this manner is equivalent to prospective medication diaries.

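### The self-report fallback for adherence is tied to leaving Highmark, not to losing sight of pharmacy claims, so a member whose drug benefit ends or who fills elsewhere has unseen days counted as unsupplied

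*Protocol*

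**What the plan says.** **Entry.** Protocol section 5.1 builds the mailing list from women with a drug benefit: "Highmark Health will identify members with prescription medication coverage who meet the following criteria". It then states "Highmark will identify a random sample of 15,000 members who meet these criteria". Section 5.1.1 makes the mailed invitation code a gate: "The code will be required to gain entry past the homepage of the study website". The stated purpose is that the step is "designed to ensure that only women invited to be in the study are able to enroll and participate". The eligibility lists themselves name membership only. Section 3.1 has "privately insured through Highmark Health", and section 4.1 has "Only members of Highmark Health will receive an invitation and are eligible to participate".

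**Measurement.** In Table 3 of section 11.2.3.2 the row "Oral contraceptives, contraceptive patch, contraceptive ring, DMPA" is scored from pharmacy claims by the medication possession ratio (MPR). Above 90% is High, 80–90% is Medium and below 80% is Low. The text defines the MPR as total days' supply divided by the number of days in the study period. Sterilization and LARC are High by assumption, and coital-dependent methods are scored by self-report.

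**Fallback.** The same section says "For participants who are no longer enrolled in Highmark, we will be unable to obtain MPR data for prescription contraceptives", and in those cases uses a six-month retrospective self-report. It gives Highmark disenrolment as 6% per year. No other trigger for self-report is stated.

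**The concern.** The measure needs visible pharmacy claims, but the fallback depends on insurer membership. The sampling filter in section 5.1 shows that the two are not the same: some members have drug coverage and some do not. A woman can therefore remain enrolled while her claims stop appearing, because the drug benefit ended or moved, or because she fills her contraceptive elsewhere. She does not meet the condition for self-report, and the MPR denominator is not limited to days with coverage. The formula then reads missing information as missing medication.

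Adherence is one of the two outcomes of Aim 2. The error can reach only women on the pill, patch, ring or DMPA. Section 3.1.2 expects the interventions to move women toward more effective methods. A woman who moves from the pill to a LARC leaves the group exposed to this error, so the error need not balance across arms even if coverage is lost at the same rate in each.

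**Working it through.** There is no figure in the protocol to reproduce on this point. The check applies the protocol's own formula and cut-offs.

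**1. A perfect user with u unseen days in a period of T days**

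MPR = (T − u)/T. High requires MPR > 0.90, and Low is MPR < 0.80 (Table 3).

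| T | u | MPR | Category |
|---|---|---|---|
| 182 | 18 | 164/182 = 0.901 | High |
| 182 | 19 | 163/182 = 0.896 | Medium |
| 182 | 36 | 146/182 = 0.802 | Medium |
| 182 | 37 | 145/182 = 0.797 | Low |
| 182 | 182 | 0/182 = 0 | Low |
| 730 | 73 | 657/730 = 0.900 | Medium |
| 730 | 147 | 583/730 = 0.799 | Low |

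Both lengths are shown because the MPR text speaks of the study period, whereas section 11.3.2 measures the outcome at four six-month points.

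**2. What the stated fallback covers**

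Disenrolment at 6% per year gives 1 − 0.94² = 11.6% over two years, or 0.1164 × 972 ≈ 113 women. These women are handled.

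**3. What it does not cover**

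The protocol gives no rate for losing claims visibility while remaining a member. Assume r = 2% to 6% per year among prescription-method users. The cumulative share affected by time t in years is 1 − (1 − r)^t.

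| Follow-up | r = 2% | r = 6% |
|---|---|---|
| 6 months | 1.0% | 3.0% |
| 12 months | 2.0% | 6.0% |
| 18 months | 3.0% | 8.9% |
| 24 months | 4.0% | 11.6% |
| Mean of the four | 2.5% | 7.4% |

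The mean is the relevant summary, because sections 11.3.1 and 11.3.2 analyse each woman's average score over the follow-up periods.

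**4. Effect on the score**

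Section 11.3.2 codes low as 1 and high as 3, so a fully adherent woman wrongly placed in Low loses 2 points.

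- r = 2%: 2 × 0.025 = 0.05
- r = 6%: 2 × 0.074 = 0.15

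This is an upper bound at each rate. It assumes that every affected woman was truly High, and that coverage lost at any time in an interval is enough to make that interval Low. In fact 37 days are needed.

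**5. Effect on an arm and between arms**

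The effect on a whole-arm mean is the figure in step 4 multiplied by the share of women on prescription methods, which is not given. If r is the same in every arm, the spurious difference between two arms is that figure multiplied by the difference in those shares. It is therefore below 0.15 for any shift in method mix, and much smaller for a modest one.

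**The case against.** The strongest reply has four parts.

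- **Entry is controlled.** A reader might infer from sections 3.1 and 4.1 that women without drug coverage can enrol. The documents do not support that. The sample is drawn only from members with coverage, and the invitation code admits only those women. This part stands in full. Adding coverage to the eligibility lists would change little, and would not detect later loss.
- **Nothing says that absent claims are scored Low.** A reader might take this as a stated rule. It is not one: it follows from applying the formula literally. The protocol's reason for the fallback, that MPR data cannot be obtained, extends naturally to loss of the drug benefit. Section 11.3.2 also has a code 0 (none) to which Table 3 assigns no MPR range, so the scoring is not fully settled here. An analysis plan, which is not at hand, may add a rule for claim-free periods. This stands as a limit on the wording. It does not remove the gap, because the protocol itself fixes the formula, the cut-offs and a single trigger. A later rule would also need coverage dates. The assent in section 6.1 names claims data and does not mention such dates.
- **The frequency is assumed.** The 6% upper end equals the disenrolment rate, which is a different event and already covered. This stands: the range is illustrative. Reading the month-24 shares of 4.0% and 11.6% as the size of the problem would also overstate it, since the analysis averages over periods.
- **Bias between arms is not shown.** Nothing ties loss of coverage to assignment. This stands. A differential effect would need both a shift in methods and an appreciable rate of lost coverage.

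Section 6.2 already asks the source of insurance coverage, which may identify some of these women. It does not ask where the contraceptive was filled.

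**Conclusion.** The point holds in a narrow form. The trigger for self-report (leaving Highmark) does not match the condition that makes the MPR unusable (claims not visible). A woman who stays a member but loses the drug benefit after the list is drawn, or who fills outside Highmark, falls between the two. Under the literal formula 37 unseen days in a 182-day interval move a perfect user to Low.

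The size is small and uncertain. On an assumed 2–6% per year, about 2.5–7.4% of prescription users are affected on average, with a fall of at most about 0.05–0.15 points in their mean score. The effect on a whole arm is smaller. The trial's primary outcome, any contraceptive use, is self-reported and untouched. Adherence belongs to Aim 2, which section 11.1 calls the secondary aim. This is a worthwhile clarification and does not threaten the trial's main conclusion.

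**What to change.** In section 11.2.3.2, tie the existing self-report fallback to claims visibility. Use it for any six-month period in which Highmark pharmacy claims are not fully visible because membership ended, the drug benefit ended, or the woman reports filling her contraceptive outside Highmark. An alternative for lost coverage is to limit the MPR denominator to days with Highmark drug coverage. That would not deal with outside fills by a woman who is still covered, so self-report would still be needed for her.

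Either way, ask Highmark to supply pharmacy-benefit start and end dates with the claims, and check that the assent wording in section 6.1 allows it.

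The cost is a sentence or two in the protocol, two date fields in the extract and one survey item on where the contraceptive was filled. The drawback is that a few more periods rest on self-report, which the plan already accepts for disenrolled women.

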#### **5.1.1. Screening Process**

The homepage of the My New Options study website will include a written and video description of the study. Women will be prompted to enter their unique invitation code at a designated spot on the study homepage if they are interested in proceeding. The code will be required to gain entry past the homepage of the study website. This authentication process is designed to ensure that only women invited to be in the study are able to enroll and participate. Potential participants will then view the study details, eligibility criteria, and the consent documents. Women who indicate interest in proceeding will be directed to REDCap (Research Electronic Data Capture), a secure, web-based application designed exclusively to support data capture for research studies (Harris et al., 2009), where eligibility will be assessed (criteria listed above).

## **5.2. Retention and Drop-out Recovery**

### **5.2.1. Identifying Secondary/Proxy Contacts**

Participants will be asked to provide study personnel with their email address, secondary email address, preferred phone number(s) (home, work, cell), and mailing address. Participants will also be asked to provide contact information for one person in case study personnel are not able to reach the participant through their provided contact information. Personal contact information is required to participate but providing a supplemental contact person is not.

### **5.2.2. Retention Promotion Efforts**

One week before participants are due for their follow up survey, they will receive an automated email letting them know that they are eligible to complete their next survey. The

email message will contain study contact information and a link to the participant's REDCap survey.

### **5.2.3. Drop-out Recovery Efforts**

If participants have not completed their scheduled survey by the date due, they will receive a series of reminders at one-week intervals as follows:

- 1st E-mail reminder that they are now due to complete their survey.
- 2nd e-mail reminder that they are due to complete their survey but time is running out. Email will also be sent to any secondary email addresses they listed at enrollment.
- Telephone call asking if participants have received our reminders and, depending upon their response, asking for an updated email address, asking them to check their junk folder, or sending them a new link.
- Text message stating that we have lost touch and asking participant to please call or email with updated contact information.
- Mailed letter stating that we have lost touch and to please call or email with updated contact information.

A final email will be sent out one week prior to taking the survey off line. The email will state that participation is very important and alert them to the fact that the survey will be taken off line by a given date.

## **5.3. Monitoring Recruitment and Retention**

### **5.3.1. Retention and Efforts to Maintain Contact with Inactive Participants**

- **Contact Person.** If we are unable to reach the participant, we will attempt to contact the participant's contact person. We will explain to the contact person how we got their name and the purpose of our call. The contact person will then be asked for updated contact information for the participant or asked to pass along a message to the participant that it is time to complete their next survey.
- **Newsletters.** Project newsletters will be sent to participants every six months approximately one month before their next scheduled survey. Each newsletter will remind participants to call or email us to update their contact information if anything has changed. Newsletters will also attempt to engage participants in study findings.

### **5.3.2. Monitoring and Quality Control of Recruitment and Retention**

The MyNewOptions Research Committee will receive monthly reports about recruitment and retention. They will closely monitor the process and provide input and suggestions as needed.

## 6. Measures and Procedures

### 6.1. Informed Consent

Signed informed consent will not be required for participation in this study because the act of voluntarily participating in the online enrollment process is considered implied consent. However, participants will be required to check a box during the eligibility process assenting to the Summary Explanation of Research document, which will describe the study in detail including the rights of the research participant and potential risks associated with study participation. This document will inform potential participants that a Certificate of Confidentiality was requested and granted by the National Institutes of Health in order to protect the research team from being forced to share court ordered information about participants. Participants will also assent by checking a box to allow Highmark Health to provide the MyNewOptions study investigators with participant contraceptive pharmacy claims and health care utilization claims occurring 6 months prior to study enrollment through the end of the 2-year study period.

### 6.2. Measures

- **Pregnancy history and pregnancy intentions and ambivalence**

We will ascertain how many times women have been pregnant in the past, as well as the outcomes of those pregnancies including number of spontaneous abortions, elective abortions, and live births. Women will be asked if they are intending future pregnancy using standard measurement, which categorizes women as intending future pregnancy, not intending future pregnancy, or ambivalent (not sure if intending future pregnancy or not). The concept of ambivalence has become increasingly important, as studies have indicated that ambivalence is associated with inconsistent contraceptive use and risk for unintended pregnancy. We hypothesize that the RLP and RLP+ interventions, which prompt women to repeatedly consider their reproductive goals, will result in decreased ambivalence. Women will also be asked how important it is to them to avoid pregnancy (very important, somewhat important, a little important, and not important) within the next year.

- **Marital and relationship history**

Relationship variables include marital/cohabiting status, relationship duration, number of sexual partners in the past 6 months, frequency of intercourse in the past 6 months ( $\geq 2x/\text{week}$ ,  $2-4x/\text{month}$ ,  $\leq 1x/\text{month}$ ), happiness with relationship, and happiness with partner's parenting (if applicable). Changes in relationship over time will be measured, as changes in partner status are expected to be key predictors of changes in pregnancy intentions and contraceptive status.

- **Sexual and contraceptive history**

Using standard measures from the NSFG, we will determine history of contraceptive methods use, as these variables have been shown to be predictors of nonadherence in previous studies.

- **Perceived control/fatalism toward contraception/preventing pregnancy**

Using a 5-point Likert scale, women will be asked if they agree/disagree with the statement, "It doesn't matter whether I use birth control or not; when it is time to get pregnant, it will happen." Our previous work has suggested that fatalism

toward contraception and preventing pregnancy may affect contraceptive adherence.

- **Health history**

Women will be asked their general health status, height/weight, perception of weight, health conditions (including conditions affecting hormonal birth control use), depression scale (PHQ-9), perceived stress scale (PSS-4), Intimate partner violence scale (HARK screen) plus reproductive coercion items (NISVS), and prescription medications contraindicated in pregnancy.

- **Health behaviors**

Women will be asked their tobacco habits and whether they have tried to quit, their alcohol consumption, physical activity (IPAQ) and their folic acid use.

- **Health care access and utilization**

Items will assess health care utilization, including seeking care for contraceptive services. Specifically, we will ask about source of insurance coverage, whether they had a contraceptive visit in the past year (if not, why not), type of place of care, type of doctor, cost constraints to seeking care and general medical care access and utilization.

- **Sociodemographic data**

For descriptive purposes, the following participant characteristics are collected: age, race, ethnicity, living situation, marital status, household composition, education, employment status, household income, occupation, and religion.

